3.3.2. Exclusion Criteria

- Patients who were included in any clinical trial for BLENREP including expanded access clinical trials
- Age $>$ 89 years of age as of start of index therapy

3.4. Variables

General descriptions of the study variables are provided below. Additional operational details will be included in the statistical analysis plan (SAP).

3.4.1. Patient Characteristics

The following patient characteristics will be measured as listed in the table below. Demographics will be summarized for the most recent measures on or prior to the index date, and all the other characteristics (i.e., clinical characteristics) will be abstracted at each clinic visit thereafter, until the end of follow-up. The end of follow-up will be defined as the date of the last clinical encounter available in the database prior to the IRB cut-off date.

Category	Variable	At Baseline	At Subsequent Clinical Encounters
Demographics	Age: Defined as of the index year.	x	
	Age groups: Patients will be assigned to one of the following age groups: 18-34, 35-44, 45-54, 55-64, 65-74, 75+.	x	
	Sex: Male, Female, Unknown	x	
	Weight	x	
	Height	x	
	Body mass index	x	

	Current Payer type: Whether the patient is covered by commercial, Medicaid, Medicare, self-insured, or was missing insurance payer type.	x	
	Race	x	
	RRMM diagnosed by DCI (yes/no)	x	
Comorbid Conditions	NCI Comorbidity Index	x	
Clinical Characteristics of RRMM	
 Subtype (e.g., IgA, IgG, light chain only, etc.) Cytogenetics Immunologic Studies Molecular testing results 	x	
Administered systemic treatments for MM prior to index	
 Medication Name Start/end dates of treatment Reason for discontinuation or change of treatment Line of therapy Prior HCST 	x	x
Treatment with BLENREP	
 Start/Re-start and end dates of treatment (as applicable) Dosing Line of therapy Reasons for discontinuation or delays of therapy 	x	x
NCCN Distress Thermometer	
 DT Score Problem List items 	x	x
Clinical Outcomes assessments	
 Myeloma markers (differs per patient and MM subtype; includes M-spike, UPEP, serum free light chains, etc.) Physician Reported Notes Disease response if available (using IMWG response criteria) Lab tests/assessments Death, if documented 		x
Ophthalmologic Status	
 Date of eye exam and results, as available. Documentation of ocular-toxicity 		x
HCRU	
 Disease-related hospitalizations Disease-related ED visits Disease-related outpatient visits 		x

3.5. Feasibility Counts/Sample Size/Power Calculation

In order to determine the feasibility of conducting the study, a query of structured EMR data was conducted in November 2021. Since January 2014, approximately 6000 patients with a corresponding ICD-9 or ICD-10 diagnosis code consistent with multiple myeloma were seen in some capacity at Duke. Approximately 30 of those patients also had a record of treatment with Belantamab mafodotin - blmf for RRMM between August 5, 2020 and Nov. 11, 2021. For this study, we would exclude patients who were included in any clinical trial, including expanded access clinical trials (approximately 2 patients). Thus, our cohort would include up to approximately 30 patients (accounting for additional patients starting on BLENREP between the proposal date and the final IRB approval date).

As the intention of this study is to be descriptive in nature to provide insight into patient characteristics, treatment patterns, and dosing, no formal hypothesis/power calculations/sample size estimates are required.

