3.3. Study Population

3.3.1. Inclusion Criteria

To be included in the final study sample, patients must meet the following inclusion criteria provided below:

- Age \geq 18 years of age as of start of treatment with Belantamab mafodotin - blmf
- Patients with a corresponding ICD-9 or ICD-10 diagnosis code consistent with multiple myeloma seen at Duke.
- Patients with a record of starting treatment with Belantamab mafodotin - blmf for RRMM between August 5, 2020 and November 22, 2022.
- Patients having healthcare encounters at DCI \geq 1-month post index

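### Does a feasibility figure of about 30 patients, drawn from a November 2021 query, conflict with an inclusion window that runs to November 2022?

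*Combined protocol and SAP*

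**What the plan says.** Section 3.5 reports a query of structured records run in November 2021. Of roughly 6000 myeloma patients seen since January 2014, it states: "Approximately 30 of those patients also had a record of treatment" with the study drug, "between August 5, 2020 and Nov. 11, 2021". About 2 of these had been in a trial or expanded-access programme and would be excluded. The section then concludes that "our cohort would include up to approximately 30 patients", a figure described as "accounting for additional patients starting on BLENREP between the proposal date and the final IRB approval date". It adds that, because the study is descriptive, no hypothesis, power or sample-size calculation is needed.

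Section 3.3.1 sets eligibility by treatment start: "Patients with a record of starting treatment with Belantamab mafodotin - blmf for RRMM between August 5, 2020 and November 22, 2022". It also requires an encounter at the centre at least one month after index, and Section 3.3.2 removes patients older than 89. Section 3.1 repeats the feasibility count and identifies November 22, 2022 as the day on which market withdrawal was requested.

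**The concern.** The count of about 30 covers the period to November 11, 2021, while the inclusion window runs about a year longer. Read literally, the stated cohort leaves room for only about two further starters in that year. Section 3.5 also ties its allowance for later starters to IRB approval, whereas Section 3.3.1 closes the window on a calendar date, so the two sections seem to end accrual at different points.

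This is the plan's only cohort-size figure, and every chart is abstracted by hand. If staff treated 30 as a ceiling, or closed the list at IRB approval, the patients left out would be the latest starters. The cohort would then be smaller than intended and tilted towards early users, in a study whose purpose is to describe real-world use.

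**Working it through.** **Inputs.** From Section 3.5: about 30 patients in the query, about 2 to exclude, and a period from August 5, 2020 to November 11, 2021. From Section 3.3.1: a window from August 5, 2020 to November 22, 2022. The documents give no count or rate for the last year, no proposal date and no IRB approval date.

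**The plan's own figure.** 30 − 2 = 28, which agrees with a stated maximum of approximately 30. The difference of 2 corresponds to 2 ÷ (28/463) ≈ 33 days of accrual at the observed rate.

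**Lengths of the periods.** The query covers 463 days and the inclusion window 839 days. The difference is 376 days, and the ratio is 839/463 = 1.81.

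**Projection at a constant rate (an assumption).** 28 × 839/463 = 50.7. Starting from 30 without the exclusion, 30 × 839/463 = 54.4. Allowing for Poisson variation in both periods at a common rate, the 95% range for the total is about 40 to 65.

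**Projection at a slower later rate (also an assumption).** At the full rate the extra year adds 28 × 376/463 = 22.7 patients.

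| Later rate as a share of the earlier rate | Total |
|---|---|
| 25% | 28 + 5.7 ≈ 34 |
| 50% | 28 + 11.4 ≈ 39 |
| 75% | 28 + 17.1 ≈ 45 |
| 100% | 28 + 22.7 ≈ 51 |

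**What a total of 30 would require.** Taking the figures at face value, 2/22.7 = 0.088, or about 9% of the earlier rate. Both inputs are rounded, however. If the query count lay anywhere from 25 to 34 (an assumed rounding range), the net count would be 23 to 32. At 23, seven more starters are needed, and (7/376) ÷ (23/463) = 0.37. At 32, none are needed. The required later rate is thus anywhere from 0 to about 37% of the earlier one, so the 9% carries little information.

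**Other filters.** The query counted patients with any treatment record. Section 3.3.1 requires a start within the window and an encounter a month later, and Section 3.3.2 applies the age limit. The plan quantifies none of these losses. In the 25% scenario, an assumed loss of 12% gives 34 × 0.88 ≈ 30.

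**Precision.** The exact 95% half-width for a proportion near 50% is about 19 points at n = 30, 16 at n = 39 and 14 at n = 51. A larger cohort narrows the intervals.

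**Do the window ends conflict?** Section 3.1 reports the withdrawal request in the past tense, so the current text was written on or after November 22, 2022. Section 5 requires IRB approval before any data collection. Final approval could therefore fall on or after the window's close, in which case the two ends are compatible. The documents do not settle this, so a contradiction is not shown.

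**The case for a change.** The best case for a change is that Section 3.5 was left behind when the window was fixed, that wording it as a maximum invites misuse, and that the cure is one paragraph and one repeat query. At a constant rate the range of 40 to 65 excludes 30, and even a quarter of the earlier rate gives 34. The Kaplan-Meier medians and confidence intervals promised in Section 3.6 depend on n, so a realistic figure would help readers and those budgeting abstraction time.

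Part of this stands. The count is stale, and the number of charts may well exceed 30. The harm does not follow, however. The IRB phrase explains what a feasibility estimate allows for; it is not an eligibility rule. Section 3.3.1 is unambiguous, Section 3.1 has data abstracted for every eligible patient, and Section 3.7 builds the initial cohort from a data-warehouse query on disease and treatment characteristics. No section caps the number or closes the list at IRB approval. Late starters would be lost only if staff disregarded those sections. The intervals will be computed from the patients actually found, whatever Section 3.5 predicted.

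**Conclusion.** The mismatch is a feasibility number that was not refreshed, and it calls for no change to the plan. The stated figure of about 30 agrees with the 28 obtained for the query period. For the full window, 34 to 51 is a reasonable range before the encounter and age filters, if later uptake was 25% to 100% of the earlier rate. The upper end rests on constant accrual, which the plan does not assert.

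Nothing rests on the 30: there is no hypothesis, power statement or stated precision target, and no analysis uses it. The cohort is defined by the inclusion and exclusion criteria, and an analyst who applies them reaches the same patients with or without a corrected figure. If the estimate is wrong, it is most likely too low, which costs abstraction time and improves precision. Updating the count would be housekeeping. It would change no eligibility rule, analysis or conclusion.

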3.6. Data Analysis Considerations

Analyses will be undertaken by Duke University statisticians with expertise in patient-centered outcomes research. Details of the analyses will be furthered described in the statistical analysis plan (SAP) to be created at a later date.

Primary Objectives: Describe patient characteristics and treatment patterns for patients treated with BLENREP

Patient demographics and clinical characteristics (including diagnosis, laboratory measurements, general symptoms, and other comorbidities) will be summarized using descriptive statistics, consisting of the mean (\pm standard deviation [SD]) and median (with interquartile range [IQR]) values for continuous variables and frequency distributions and proportions for categorical variables.

Demographics will be described for the most recent measures on or prior to the index date. Clinical outcomes will be described until the end of follow-up. The end of follow-up will be defined as the date of the last clinical encounter available in the database prior to the IRB cut-off date. Summary statistics such as mean (\pm SD) and median (with IQR) values for continuous variables and frequency distributions and proportions for categorical variables will be calculated.

Time to clinical outcomes (i.e., time to response, duration of response, OS) will be analyzed using Kaplan-Meier analysis and median times to event will be reported (if the medians are achieved). 95% CIs will be reported in addition to the medians.

Treatment use and treatment patterns will be summarized using proportions (i.e., proportion of patients with select treatment for the control of symptoms). Sequences of treatment will also be described.

Secondary Objective: Describe Ophthalmology visit patterns and events

To the extent that they are available, events related to Ophthalmology outcomes (i.e., eye exams, outpatient visits, treatments for ocular toxicity, and other related HCRU events) will be summarized by the mean (\pm SD) and median (with IQR) number of events per patient per year and by the proportion and frequency distribution of patients with any occurrence of the respective

outcome. Treatment use and treatment patterns associated with ocular toxicity will be summarized using proportions (i.e., proportion of patients with select treatment for the control of symptoms).

Secondary Objective: Explore magnitude and sources of distress for these patients

The main outcome variable is the occurrence of actionable distress, defined as a NCCN DT score of 4 or higher. This outcome is clinically relevant because it is aligned with the medical practice guidelines for management of distress in cancer patients. The analysis will describe the proportion of clinic visits where actionable distress is reported during treatment with BLENREP, and the frequency of actionable distress over time.

Sources of distress will be assessed using the NCCN DT Problem List by examining the proportion of visits where types of problems are reported (e.g., physical or emotional problems). The frequency of individual types of problems, and the most commonly-reported problems will be examined descriptively.

Secondary Objective: Describe healthcare resource utilization (HCRU)

To the extent that they are available, HCRU (i.e., inpatient admissions, treatment-related outpatient visits, and emergency department visits) will be summarized by the mean (\pm SD) and median (with IQR) number of events per patient per year and by the proportion and frequency distribution of patients with any occurrence of the respective outcome. Likewise, mean (\pm SD) and median (with IQR) length of stay per year will be summarized for inpatient visits.

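### Does ending follow-up at the last clinical encounter remove recorded deaths from the overall survival analysis?

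*Combined protocol and SAP*

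**What the plan says.** Sections 3.4.1 and 3.6 of the protocol give the same end of follow-up: "defined as the date of the last clinical encounter available in the database prior to the IRB cut-off date". Section 3.6 adds: "Clinical outcomes will be described until the end of follow-up". The next paragraph names OS: "Time to clinical outcomes (i.e., time to response, duration of response, OS) will be analyzed using Kaplan-Meier analysis", with medians (where reached) and 95% confidence intervals.

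Section 3.4.1 says that characteristics other than demographics "will be abstracted at each clinic visit thereafter, until the end of follow-up". Its table has two timing columns, one for baseline and one headed "At Subsequent Clinical Encounters". The clinical outcomes row, which holds myeloma markers, physician notes, response, laboratory tests and "Death, if documented", is marked only in the second.

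No section defines the OS event, the OS start date or the censoring date, and the IRB cut-off is named without a calendar date. Sections 3.4 and 3.6 leave operational and analytic detail to a SAP that had not been written when this text was issued.

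**The concern.** A last-encounter limit suits outcomes measured at visits, such as response. Death is different. A patient who dies at home or in another hospital has no later encounter here, so the date of death falls after the end of follow-up as defined. If the limit is applied mechanically, that patient leaves the risk set alive at the last visit, and leaves because of the approaching death. Such censoring is informative, it pushes the Kaplan-Meier curve upward only, and the confidence interval does not reflect it.

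Clinical outcomes fall under a primary objective (section 2.1), and with no comparator the OS estimate is itself the result. The rule also governs abstraction, so one could fear that the relevant death dates would never be collected.

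**Working it through.** **Step 1. The passages side by side.** The documents state no OS figure, so there is nothing to reproduce, and the question is first one of reading.

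- The follow-up definition says when observation of a patient ends. For a patient not known to have died, the last encounter is roughly the date last known alive, which is the usual OS censoring date.
- Death is listed as a variable to collect, conditional only on documentation. Nothing requires it to be documented during a visit.
- The table column is the only post-baseline column. Death cannot be a baseline item, so its place there says nothing about deaths between or after visits.
- No sentence says that a patient with a documented death is censored. That result needs the general follow-up limit to override a specifically collected event.

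**Step 2. Size if the limit were applied mechanically.**

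Inputs from the protocol: up to about 30 patients (section 3.5); index dates from August 5, 2020 to November 22, 2022, or 27.6 months (section 3.3.1); and the criterion "Patients having healthcare encounters at DCI" at least 1 month after index (section 3.3.1), read here as survival to such an encounter.

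Assumed, because the documents do not give them: exponential OS with a true median of 12 months, monthly visits, a cut-off 12 months after the index window closes, and a share p of deaths dropped and censored at the preceding visit.

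Dropping a share p of deaths multiplies the apparent hazard by (1 − p), so the apparent median is about 12/(1 − p). With monthly visits the first encounter at or after 1 month falls between 1 and 2 months, on average at 1.5. Because exponential survival has no memory, the entry criterion adds about 1.5 months: 1.5 + 12/(1 − p).

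| p | 12/(1 − p) | Simulated, no entry criterion | 1.5 + 12/(1 − p) | Simulated, with criterion | 12-month OS, with criterion |
|---|---|---|---|---|---|
| 0% | 12.0 | – | 13.5 | 13.5 | 55% |
| 10% | 13.3 | 13.3 | 14.8 | 14.7 | 58% |
| 20% | 15.0 | 14.9 | 16.5 | 16.3 | 61% |
| 30% | 17.1 | 16.9 | 18.6 | 18.3 | 65% |
| 50% | 24.0 | 23.4 | 25.5 | 24.8 | 73% |

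The step from 12 to 13.5 months comes from the entry criterion, not from the follow-up rule. It is larger than the effect of losing 10% of deaths (14.7 − 13.5 = 1.2 months).

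**Step 3. Sampling error at 30 patients.** In simulated cohorts of 30 with no death dropped (about 22 deaths), the central 95% of Kaplan-Meier medians runs from 8.8 to 21.4 months, a width of 12.6. A hand check, ignoring censoring before the median:

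- standard error of S at the median: √(0.25/30) = 0.091
- density there: 0.5 × ln 2/12 = 0.0289 per month
- standard error of the median: 0.091/0.0289 ≈ 3.2 months
- 95% width: 2 × 1.96 × 3.2 ≈ 12.5 months

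A 30% loss (0.30 × 22 ≈ 6.6 deaths) gives 18.3 months, inside that range. A 50% loss gives 24.8, outside it.

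**Step 4. Size if recorded deaths are counted.** Under the same assumptions the median is 13.5 months with regular visits, so there is no shift. If 20% or 40% of patients leave the network, and survivors among them are censored at last contact while later deaths are still recorded, it is 13.2 or 12.8. That is a downward shift of 0.3 or 0.7 months.

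**The case for a change.** The strongest opposing case is that the text sets one limit for all clinical outcomes, names OS among them and exempts nothing. Two careful abstractors could therefore differ, and a reader of the report could not tell which convention was used. The error runs in one direction only, so falling within sampling error does not make it harmless. A second simulation at 30 patients, on different assumptions, shows the same mechanism. With a true median of 12 months, the typical estimate is 11.7 months if all deaths count, against 15.4 if the 25% of deaths outside an encounter are dropped. At 50% it is 22.7, and the median is not reached in 34% of cohorts, against 1%. The Limitations section mentions non-random missing data in general but not missed deaths.

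The silence of the text and the direction of the bias stand. The likelihood and permanence of the error do not. Large losses require someone to see a death date in the chart and disregard it in an analysis of survival. Nothing in the documents supports any particular share of deaths lost, so both simulations show a mechanism and not an expected error. The data are not lost either: this is a retrospective review of about 30 existing charts, and a recorded death date stays there to be read. Section 3.7 describes a case report form piloted and revised to catch unforeseen situations. Deaths that never reach the record are missed under either reading, so they do not bear on this rule.

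**Conclusion.** The plan leaves an event and censoring convention unwritten; it does not prescribe a wrong one. The natural filling is the standard one: a documented death up to the cut-off is an event on its date, and everyone else is censored when last known alive. The plan already collects the death variable and a last-contact date, and it places detail of this kind in the later SAP. On that reading the bias is nil with regular visits, and at most 0.7 months downward if up to 40% of patients leave the network.

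The upward bias arises only if recorded deaths are set aside. Its size rests wholly on assumed inputs, and for losses up to 30% of deaths the resulting median stays within the sampling range of a cohort of 30. The study is descriptive and exploratory, OS is one of several outcomes reported as available, and no test depends on it. This is a gap that analysts fill sensibly, and no change to the plan follows.

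### Time to response by Kaplan-Meier, with no stated stop at next therapy and death not treated as competing, can yield a median although fewer than half respond to BLENREP

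*Combined protocol and SAP*

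**What the plan says.** Section 3.6 of the protocol names one method for three endpoints: "Time to clinical outcomes (i.e., time to response, duration of response, OS) will be analyzed using Kaplan-Meier analysis". It adds that "median times to event will be reported (if the medians are achieved"), with 95% confidence intervals.

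The observation window is general: "Clinical outcomes will be described until the end of follow-up". Sections 3.4.1 and 3.6 define its end in the same way: "The end of follow-up will be defined as the date of the last clinical encounter available in the database", before the IRB cut-off. The window is not tied to the end of BLENREP or to the start of another therapy.

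The table in Section 3.4.1 collects "Disease response if available (using IMWG response criteria") at subsequent encounters, without limiting it to the BLENREP line. Section 3.6 also promises that "Sequences of treatment will also be described", but does not link those sequences to response.

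The documents do not give a time origin, an analysis population, a rule for next therapy or a rule for death without response. Detail is deferred: Section 3.4 says "Additional operational details will be included in the statistical analysis plan (SAP"), and Section 3.6 says "Details of the analyses will be furthered described in the statistical analysis plan (SAP) to be created at a later date".

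**The concern.** Two mechanisms push the curve up if the text is applied to all treated patients.

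- **Later-line credit.** A patient who does not respond to BLENREP, moves to another therapy and responds to that one has a response recorded before the last encounter. Nothing stops it counting as an event. Later therapy within follow-up is plausible: BLENREP starts are accepted up to the day on which market withdrawal was requested (Sections 3.1 and 3.3.1), and Section 1 describes frequent ocular toxicity. By contrast, Section 3.6 limits the distress analysis to the period on BLENREP.
- **Death as censoring.** Kaplan-Meier by default censors a patient who dies without response, as if that patient could still respond. One minus the estimate then exceeds the probability of responding.

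Describing clinical outcomes is a primary objective (Section 2.1), and there is no control group (Section 4). With up to about 30 patients, a few events decide whether the curve crosses 50%. A reader who sees a median time to response in all treated patients will infer that at least half responded to BLENREP.

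**Working it through.** **The plan's own figure.** Section 3.5 starts from about 30 patients and excludes about 2 trial patients: 30 − 2 = 28. With later starters added, this agrees with its cohort of up to about 30. No power or sample-size figure applies.

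**Mechanism, in a constructed cohort of 28 (all values assumed).**

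- 9 respond to BLENREP, at months 1, 1, 1, 2, 2, 2, 3, 3 and 4.
- 8 die without response or next therapy, at months 2.5, 3.5, 3.5, 4.5, 5.5, 6.5, 7.5 and 8.5.
- 11 start next therapy at months 2.5 to 4.5. Of these, 6 respond to it (months 5, 5, 6, 6, 7, 8), 2 die (months 10 and 12) and 3 are alive at month 18.

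As written, S(t) = ∏(1 − d/n), with deaths censored and every response counted:

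| Month | At risk n | Responses d | 1 − d/n | 1 − S |
|---|---|---|---|---|
| 1 | 28 | 3 | 25/28 | 10.7% |
| 2 | 25 | 3 | 22/25 | 21.4% |
| 3 | 21 | 2 | 19/21 | 28.9% |
| 4 | 17 | 1 | 16/17 | 33.1% |
| 5 | 15 | 2 | 13/15 | 42.0% |
| 6 | 12 | 2 | 10/12 | 51.7% |
| 7 | 9 | 1 | 8/9 | 57.0% |
| 8 | 7 | 1 | 6/7 | 63.2% |

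A median of 6.0 months is reported, although 9/28 = 32.1% responded to BLENREP. Cumulative incidence (Aalen-Johansen), F(t) = Σ S(u−)·d/n with S the probability of being free of all three events, takes death and next therapy as competing. It gives 9/28 = 32.1%, and the median is not reached. Counting only BLENREP responses but still censoring deaths gives 33.1%, so in this example later-line credit does most of the damage.

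**Size, by simulation of cohorts of 30.** The documents give no response, switching or survival rates. The assumptions are:

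- time to response gamma (shape 2, scale 0.9 months; median about 1.5 months);
- median survival of non-responders/responders 12/12, 9/18 or 6/24 months;
- administrative follow-up uniform on 6–33 months;
- next therapy in non-responders exponential with median 4 months, and later response with the same gamma delay;
- the Section 3.3.1 requirement of encounters at least one month after index, modelled as survival of at least one month.

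Mild later-line credit means that 50% of non-responders would switch and 10% of those respond. Strong means that 70% would switch and 20–30% of those respond.

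Share of cohorts that report a median with fewer than 15 BLENREP responders:

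| Assumed true response | Death censoring only | Mild credit | Strong credit |
|---|---|---|---|
| 40% | 2–9% | 12–19% | 31–47% |
| 30% | 1–2% | 4–7% | 17–33% |
| 20% | about 0% | about 1% | 5–15% |

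A repeat run agreed to within about 3 percentage points, so the entries are approximate. The one-month requirement matters because it removes the earliest deaths: without it, the 40% row would read 6–19%, 16–28% and 35–54%.

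**With cumulative incidence instead** (run without the one-month requirement), the curve reached 50% with fewer than 15 BLENREP responders in 0.0% of cohorts. With shorter follow-up (1–28.6 months) the figure was 1.1–1.2%. The remedy is close to complete but not absolute.

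**The case against.** **The plan is silent; it has not decided.** A reader might infer that the protocol instructs analysts to credit later-line responses to BLENREP. It does not. The end of follow-up is a general observation window, and operational detail is deferred. This stands: the SAP can settle the matter. But the estimator and the reporting rule are already named, and a SAP that simply follows Section 3.6 inherits both mechanisms.

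**The population is not stated.** If time to response is computed among responders only, its median does not imply that half responded. This also stands, and the size figures apply only to the all-treated reading. A responder-only median is always available however few respond, so it needs the response proportion beside it.

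**A stop rule alone might do.** In the constructed cohort, Kaplan-Meier with censoring at death and next therapy gives 37.1% against 32.1%, with no median. In a second set of simulations it still gave a median with under half responding in 0–34% of runs (n = 28, response 20–40%, 40–80% of non-responders switching, 20–60% of those responding, median survival about 9 months). The change of estimator is more than preference.

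**Duration of response and overall survival.** A reader might infer that these are wrong too, since the same sentence covers them. The documents do not support that. Their event and censoring rules are simply not yet written, and every charted death may well be meant to count. They are requests for clarification, not part of this point.

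**The study is descriptive.** No test or decision rule depends on this median, which limits the severity.

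**Conclusion.** The point holds, as a minor one. Applied to all treated patients, Section 3.6 as written permits a median time to response when fewer than half respond to BLENREP. The frequency runs from about 0% of cohorts (20% response, death censoring only) to about 47% (40% response, strong later-line credit). These figures rest on assumed response, switching and survival rates. The effect is small if true response is well below half and few patients switch or respond later. If the SAP ends the response window at next therapy without leaving those patients at risk of a BLENREP response, mainly the death-censoring part remains: about 2–9% at 40% response.

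It would go too far to conclude that next-therapy dates will not be collected. The non-BLENREP therapy row in Section 3.4.1 is titled as pre-index treatment, yet it is also ticked at subsequent encounters and includes start and end dates. The label needs reconciling; it does not show that the data will be missing.

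**What to change.** In the SAP:

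1. Define response as the first IMWG response from the index date to the start of next myeloma therapy, with all treated patients as the denominator.
2. Replace Kaplan-Meier for time to response with cumulative incidence, taking death without response and next therapy as competing events. A simpler alternative is the proportion responding before next therapy.
3. With either, report the median time to response among responders, labelled as such and with the number of responders.

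In the case report form, reconcile the title of the prior-therapy row with its tick under subsequent encounters, so that the next-therapy start date is abstracted. Abstraction is manual, so settling this beforehand avoids returning to the charts.

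The cost is SAP wording, standard code and possibly one date field. The response figure may be less favourable, and an all-patient median time to response will often no longer be reported.
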